7.5.3 Serious Unexpected Adverse Drug Reactions

A serious adverse drug reaction means a noxious and unintended response to a drug that occurs at any dose and that requires in-patient hospitalization or prolongation of existing hospitalization, causes congenital malformation, results in persistent or significant disability or incapacity, is life-threatening or results in death. An adverse drug reaction is considered unexpected when its nature (i.e., specificity or outcome), severity or frequency is either not identified, or is not consistent with the term or description used in the product labelling.

7.5.4 Adverse Event Reporting

Clinical sites are responsible for reporting SAEs and serious unexpected adverse drug reactions immediately to the Methods Center via the REDCap Cloud system. Significant new information on ongoing SAEs should also be provided promptly to the Methods Center via the REDCap Cloud system. Unanticipated problems resulting in risk to participants or others are also to be reported promptly to the Methods Center.

The Methods Center will inform all applicable regulatory agencies of any serious unexpected adverse drug reaction in respect of the drug that has occurred as follows:

- (a) if it is neither fatal nor life threatening, within 15 days after becoming aware of the information; and
- (b) if it is fatal or life threatening, within seven days after becoming aware of the information.

Within eight days after having informed the regulatory agency of any serious unexpected adverse drug reactions, the Methods Center will submit to the regulatory agency a complete report in respect of that information that includes an assessment of the importance and implication of any findings made.

Adverse drug reactions that are expected or unexpected, but not serious, will not be reported to the regulatory agency, but rather monitored and tracked by the Methods Center. The Methods Center will report to applicable regulatory agencies "expected, serious" adverse drug reactions, where an increase in the rate of occurrence or severity, was judged to be clinically important.

A causality assessment will be undertaken by the Methods Center, together with the responsible investigator for clinical investigation cases, and any case judged as having a reasonable suspected causal relationship to the medicinal product will be reported.

7.5.5 Clinical Site Reporting – IRB and REB

Clinical sites are responsible for reporting SAEs and unanticipated problems resulting in risk to participants or others to their local REB/IRB or the Central IRB in accordance with local reporting requirements. Copies of each report and documentation of ethic board notification and receipt will be kept in the clinical site's study file.

7.5.6 Data and Safety Monitoring Committee

As per the FDA guidance document the *Establishment and Operation of Clinical Trial Data Monitoring Committees for Clinical Trial Sponsors*, a Data and Safety Monitoring Committee will oversee the safety of the trial participants and the overall conduct of the trial. The members of the Data and Safety Monitoring Committee will include two orthopaedic surgeons, an infectious disease expert, a biostatistician and a fracture patient representative. One orthopaedic surgeon will act as the Chair of the Committee. The Data and Safety Monitoring Committee will be responsible for safeguarding the interests of study participants, assessing the safety and efficacy of study procedures, and for monitoring the overall conduct of the study. The Data and Safety Monitoring Committee will frequently review enrollment and demographic summaries, listings of protocol deviations, and summaries and listings of SAEs. They will advise the Principal Investigators and study team on any concerns related to participant safety and trial conduct, and will make recommendations for the study to continue as designed, for study termination, for study continuation with major or minor modifications, or temporary suspension of enrollment until some uncertainty is resolved. We will develop a Data and Safety Monitoring Committee charter to guide the process.

7.6 Dissemination Policy

The results from each fracture population will be submitted for publication regardless of whether there are significant findings. Every attempt will be made to ensure that the amount of time between completion of data collection and release of study findings are minimized.

8.0 SUB-STUDY: PATIENT EXPERIENCES IN THE AQUEOUS-PREP AND PREPARE TRIALS

8.1 Introduction

Patient and stakeholder involvement in the design of randomized controlled trials is increasingly becoming recognized as an essential component of a trial's success.^{58,59} Patient and stakeholder involvement (PSI) has been seen as the paradigm shift from research being done "to" or "for" patients, to research being performed "with" or "by" patients themselves.⁶⁰ PSI allows for democratization of the research process and empowering patients throughout the entire research process – from design through to knowledge dissemination.⁶¹ Research has found that patients and stakeholders are motivated to be involved in research for a wide variety of reasons, including a desire to contribute to research for the benefit of others.⁶²

Prior research has argued that PSI enhances the focus of clinical trials on outcomes that are relevant to patients themselves, thus increasing the utility of any research findings.⁶³ Furthermore, PSI has been argued to improve recruitment and retention rates, while raising the quality of research findings and ultimately helping with the dissemination of research findings.⁶⁴ Lastly, PSI may be able to improve patient safety when patients are involved in safety reporting in hospital settings.⁶⁵

Despite these findings, a recent systematic review estimates that far less than 1% of clinical trials engage patients in any meaningful or active way.⁶⁶ From the onset of the PREP-IT trials (i.e. the Aqueous-PREP and PREPARE trials), the PREP-IT investigators have engaged multiple patient-partners and stakeholders in the design, conduct, and implementation of the PREP-IT trials. One of our engagement goals is to identify ways in which we can better engage with PREP-IT study participants. To support this goal, we seek to learn about PREP-IT participants' experiences within the PREP-IT trials. This knowledge will be used to improve the study team's ability to engage study participants and provide study information in a meaningful and accessible manner. Additionally, the unique design of the PREP-IT trials (e.g., consent after the intervention, minimal follow-up, minimal requirements for participants) provides a novel trial to investigate this question. This led to the current sub-study.

8.2 Rationale and Objectives

One of the mandates of the PREP-IT program is to improve orthopaedic fracture research through meaningful engagement with our patient-partners and stakeholders. The objective of this sub-study is to learn about PREP-IT participants' experiences with participating in the Aqueous-PREP or PREPARE trial. The results of this sub-study will be used to develop strategies to better engage research participants both in the PREP-IT trials as well as in future clinical trials.

8.3 Sub-Study Design

This sub-study will consist of an exit survey that will be given to a subset of participants in the PREP-IT trials. Select clinical sites participating in the Aqueous-PREP and / or PREPARE trial will be invited to participate in the sub-study.

The exit survey is comprised of 14 questions that includes multiple choice and brief open-ended questions. All of the questions use clear and simple language written at or below a grade eight reading level to enhance the validity of results. The survey length has been kept to a minimum to maximize response rate and limit barriers that would affect its proper completion.

The survey was created after reviewing the current literature and with input from the PREP-IT investigators, research coordinators, patient-partners, and stakeholders. Engaging the larger study team follows the PREP-IT philosophy of meaningful engagement, as well as helps to ensure that no vital questions were missed and that the survey wording is clear and easily understandable to the target audience. The questionnaire was pre-tested on a sample of convenience.

8.4 Survey Participants and Distribution

All potential substudy participants, or their proxies, will be required to provide informed consent specifically for the substudy prior to completing the survey. Informed consent for the substudy may be obtained at the time of enrollment in the Aqueous-PREP or PREPARE trial using procedures described in sections 4.3.1 and 7.2, or in-person at a subsequent follow-up visit or time of survey administration using a pen and paper consent form. The patient or proxy must be provided with a copy of the signed informed consent form. All sites within the United States of America must conduct their consenting process in accordance with HIPAA (Health Insurance Portability and Accountability Act) regulations as approved by their institutions, and sites in Canada must comply with the Personal Information Protection and Electronic Documents Act (PIPEDA).

Clinical sites participating in the sub-study will offer the survey to all eligible participants at the time they complete their one-year follow up visit. The survey will be sent to participants either through mail, email or RedCap Cloud, given to them on paper at a follow-up visit, or administered over the phone, depending on each individual participant's preference. The Research Coordinator may also telephone or text the participant to remind them to complete the exit survey. We will document the number of participants invited to participate in the survey as well as the number of participants who decline participation.

8.5 Data Entry

The exit survey responses will be entered into the Aqueous-PREP / PREPARE trial's electronic data capture (EDC) system.

8.6 Sample Size

Sample size was calculated using a 5% margin of error, with 95% confidence intervals, a potential population of all patients who have completed one year follow up (approximately 1600 patients) and an expected response rate of 50%. With this in mind, a sample size of approximately 310 patients who complete every survey question will be required.⁶⁷ As such, the survey will be distributed to all participants at participating clinical sites until our sample size of at least 310 participants is achieved.

8.7 Data Analysis

We will summarize all variables with frequencies and percentages. The short form questions will be coded appropriately based on themes.

8.8 Anticipated Implications of Results

This research serves as an important step towards understanding patients' perspectives as participants in a clinical trial. Additionally, the research may influence how future clinical trials are designed and conducted, with the overall goal of a greater focus on the patient experience and increasing patient involvement in research. Lastly, the results of this sub-study could help the study team to develop aids (e.g., posters, pamphlets, etc.) to improve patients' understanding of clinical research and overall experience with the PREP-IT trials.

9.0 SUB-STUDY: THE IMPACT OF HETEROTOPIC OSSIFICATION PROPHYLAXIS AFTER SURGICAL FIXATION OF ACETABULAR FRACTURES: NATIONAL TREATMENT PATTERNS AND RELATED OUTCOMES

9.1 Introduction

Heterotopic ossification (HO) is a common complication after surgical fixation of acetabular fractures, with incidence rates reported as high as 90%.⁶⁸⁻⁷¹ HO can be a debilitating complication and surgical excision for more severe cases carries a high complication rate.⁷² Numerous strategies have been employed to prevent HO formation but results are mixed and the optimal treatment strategy remains controversial.

The most common modalities used to prevent HO formation are oral administration of indomethacin or single-dose external beam irradiation therapy (XRT).^{68,73-77} Despite the common use of indomethacin and observational data to support its use,^{76,77} more recent randomized controlled trials (RCTs) have failed to demonstrate any significant reduction in the incidence of severe HO when patients were administered indomethacin versus placebo.^{78,79} Similarly, XRT has

been shown to be effective against HO formation in smaller observational studies, but there are no adequately powered RCTs to support its use compared to placebo.^{68,75} Additionally, there remain concerns with the use of XRT as it relates to cost (over 200 times that of indomethacin), risk of radiation-induced sarcoma, and increased rates of non-infectious wound healing problems.⁸⁰⁻⁸³

9.2 Rationale and Objectives

Given the high incidence, impact on outcomes, and controversy regarding treatment, there remains a need for continued research to determine optimal treatment strategies for HO prophylaxis after posterior acetabular surgery. The PREPARE trial cohort is an ideal opportunity to evaluate variations in practice treatment patterns across a wide range of clinical sites. The primary objective of this sub-study is to describe national HO prophylaxis treatment patterns after posterior acetabular fracture surgery. Secondarily, we will determine the association between treatment modalities – indomethacin, XRT, or no prophylaxis – and the prevalence of HO formation after acetabular fracture surgery.

9.3 Sub-Study Design

This sub-study will include a subset of participants in the PREPARE trial. All clinical sites participating in the PREPARE trial that enrolled patients with closed AO-type 62 fractures will be invited to participate in the sub-study.

From the participant's medical record, we will obtain data related to the injury characteristics of the fracture, the surgical approach at time of fixation, and any notable HO present on follow-up radiographs. HO on follow-up radiographs will be measured and classified as described by Brooker *et al.*⁸⁴ These data fields were selected after reviewing the current literature and with input from the PREPARE investigators. A virtual meeting was held to engage participating sites and ensure that no vital questions were missed and that the language is clear and easily understandable.

All potential sub-study participating clinical centers will be identified by their enrollment of patients with closed AO-type 62 acetabular fractures. The CRF will be distributed to all sites with eligible participants.

9.4 Data Entry

The CRF responses will be entered into the PREPARE trial's electronic data capture (EDC) system.

9.5 Sample Size

A statistical power analysis was performed for sample size estimation based on previous data.⁷⁵ With an alpha = 0.05, power = 0.80, and allocation ratio of 1, the projected total sample size needed to detect between group differences was 58 patients with Brooker III/IV as an endpoint and 156 patients with Brooker IV as an endpoint.⁸⁵

9.6 Data Analysis

We will summarize all variables with frequencies and percentages. Multivariable regression analyses will be performed to evaluate the association of HO formation by HO prophylaxis modality. These models will be stratified by fracture classification and adjusted for predictors of HO formation including Injury Severity Score (ISS).

9.7 Anticipated Implications of Results

We hypothesize that despite the limited evidence to support the use of indomethacin as an effective HO prophylaxis strategy, many centers still utilize this treatment protocol. We also anticipate to find that HO prevention strategies such as XRT and indomethacin are not associated with the severity of HO formation as compared to a no prophylaxis control group.

To our knowledge, this study will be the largest of its kind and will also be the first to reveal HO prophylaxis patterns on a national level. These data will both help inform the orthopaedic trauma community on best practices and potentially decrease the burden of HO formation after posterior acetabulum fracture surgery.

10.0 SUB-STUDY: MEASUREMENT OF TROPONIN FOLLOWING FRACTURE REPAIR SURGERY

10.1 Introduction

Myocardial injury after noncardiac surgery (MINS) is defined as an acute elevation of troponin due to myocardial ischemia occurring during or within 30 days after noncardiac surgery. Diagnostic criteria for MINS include patients that fulfill the Universal Definition of Myocardial Infarction (MI), and patients with ischemic troponin elevation without any ischemic feature (e.g., chest pain or ischemic electrocardiographic findings).^{86,87} Specifically, MINS is defined as a postoperative peak level of non-high-sensitivity troponin T (TnT) of 0.03 ng/mL or greater,⁸⁷ or a postoperative peak of high-sensitivity troponin T (hsTnT) of 20 to <65 ng/L with an absolute change of ≥ 5 ng/L or a postoperative peak of hsTnT ≥ 65 ng/L with no evidence of a non-ischemic etiology (such as rapid atrial fibrillation, sepsis, or pulmonary embolism).^{86,88,89} Those thresholds were determined to be independently associated with death at 30 days. A high-sensitivity troponin I (hsTnI) ≥ 60 ng/L (ARCHITECT STAT Abbot assay),⁸⁸ and a hsTnI ≥ 75 ng/L (Siemens Healthineers ADVIA Centaur Assay)⁸⁹ are also associated with major cardiovascular events 30 days after noncardiac surgery, and are suggested as thresholds for MINS. For other troponin assays, physicians should consider any elevation above the 99th percentile upper reference limit.⁸⁶

Recent research has found that MINS is common in certain patients undergoing orthopaedic surgery. The VISION orthopaedic sub-study, a large prospective cohort study, identified that among patients ≥ 45 years of age who had orthopaedic surgery 11.9% (367/3092) had MINS.⁹⁰ This study also demonstrated that MINS was independently associated with 30-day mortality in this population. Specifically, orthopaedic patients without and with MINS had a 30-day mortality rate of 1.0% and 9.8%, respectively (odds ratio [OR], 11.28; 95% confidence interval [CI], 6.72 to 18.92). Importantly, the 30-day mortality rate was increased for patients with MINS who had an ischemic feature (i.e., symptoms, or evidence of ischemia on electrocardiography or imaging) (OR, 18.25; 95% CI, 10.06 to 33.10) and for those who did not have an ischemic feature (OR, 7.35; 95% CI, 3.37 to 16.01). The proportion of orthopaedic patients with MINS who were asymptomatic and in whom the myocardial injury would have probably gone undetected without serum troponin monitoring was 81.3% (95% CI, 76.3% to 85.4%).

Based on these recent findings (Thomas, JBJS 2020)⁹⁰, there is a strong rational for routine perioperative screening of troponin levels in fracture surgery patients. Supporting those results, the Canadian Cardiovascular Society (CCS) Guidelines,⁹¹ the European Society of Cardiology (ESC)⁹² and the most recent Universal definition of MI statement⁸⁶ also recommend that higher risk patients undergoing noncardiac surgery should be routinely monitored for MINS.

10.2 Rationale and Objectives

It remains unknown if standard perioperative troponin monitoring is incorporated in routine clinical practice in fracture patients requiring surgical management. Thus, the prevalence of MINS, and its associated mortality, is unknown in this population. The VISION orthopaedic study primarily included patients undergoing elective orthopaedic procedures (e.g. hip and knee replacements). Fracture patients may be at higher risk, considering they undergo urgent surgery. The VISION study demonstrated that urgent and emergent surgeries are associated with higher mortality than elective surgeries.⁸⁸ Moreover, the HIP ATTACK trial demonstrated that myocardial injury after randomization happened in 901/2970 (30.3%) hip fracture patients with routine postoperative troponin screening performed.⁹³ There is biological plausibility and evidence from large cohort studies⁹⁴ to support that fracture patients have higher incidence of postoperative adverse outcomes, including MINS, as the physiologic stress of the fracture (e.g., inflammation, bleeding, catecholamine release) may contribute to clinical complications such as an acute myocardial injury.

Therefore, the objective of this sub-study is to determine the proportion of PREPARE participants ≥ 45 years of age who have perioperative troponin levels measured as part of their standard of care.

10.3 Sub-Study Design

All clinical sites participating in the PREPARE trial will be invited to participate in the sub-study. This sub-study will include a subset of participants in the PREPARE trial: 1) participants enrolled after 1-February-2020 and 2) participants ≥ 45 years of age.

Study personnel will document the following in the case report forms:

1. Whether any serum troponin levels were ordered between the perioperative window of hospital admission to postoperative day 3, inclusive.
2. All dates, times, and serum troponin concentration levels, troponin type (e.g., TnT, hsTnT, hsTnI) and assay used, and upper reference limit, during the perioperative window of interest.
3. Evidence of ischemic etiology associated with elevated troponin results.

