10.4 Sample Size

We anticipate that data from 1,000 PREPARE participants will be included this sub-study. Sample size will be driven by the number of sites willing to participate in this sub-study, as well as the number of patients enrolled before enrollment for the parent PREPARE trial closes. Assuming the incidence of measuring serum troponin levels is 10% among study participants, a sample size of 1,000 patients will ensure the precision of this estimate is within 2% (95% confidence interval 8%-12%).

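### The troponin sub-study's stated precision of within 2% treats patients as independent and makes no allowance for clustering within the volunteering hospitals

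*Protocol*

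**What the plan says.** The troponin sub-study (Protocol section 10) sets out to estimate the proportion of participants aged 45 or over whose perioperative troponin is measured in usual care. Section 10.2 gives the motive: "It remains unknown if standard perioperative troponin monitoring is incorporated in routine clinical practice in fracture patients requiring surgical management".

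On size, 10.4 Sample Size says "We anticipate that data from 1,000 PREPARE participants will be included this sub-study". It sets the working proportion ("Assuming the incidence of measuring serum troponin levels is 10% among study participants") and concludes that "a sample size of 1,000 patients will ensure the precision of this estimate is within 2% (95% confidence interval 8%-12" (the upper limit being 12%). The same section says "Sample size will be driven by the number of sites willing to participate in this sub-study", and 10.3 says "All clinical sites participating in the PREPARE trial will be invited to participate in the sub-study". Section 10 states no ICC, design effect or number of sub-study sites.

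On data, item 1 of 10.3 records "Whether any serum troponin levels were ordered between the perioperative window of hospital admission to postoperative day 3, inclusive". Item 2 collects the date, time and level of every troponin in that window. In 10.1, "MINS is defined as a postoperative peak level" of troponin, with assay-specific thresholds. Section 10.5 leaves the analysis to a sub-study SAP still to be written and describes the work as mainly descriptive.

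**The concern.** Patients enter this sub-study through hospitals, and the hospitals choose whether to join. It is plausible, though the documents do not say so, that ordering troponin follows local practice, so that two patients at one hospital are more alike than two patients at different hospitals. If so, 1,000 patients carry less information than 1,000 independent ones, and an interval that ignores this is too narrow. The parent trial's own sample size allows for between-hospital variance in infection (Protocol 5.1); the sub-study allows for none, yet words its precision as assured.

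At stake is how firmly the estimate can be used in planning the later cohort study described in 10.6. A range of 8% to 12% supports tighter planning than, say, 5% to 15%.

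**Working it through.** **Inputs.** n = 1,000, p = 0.10 and the 95% interval of 8% to 12% come from Protocol 10.4 Sample Size. The number of sub-study sites is not given. I use 18 (parent-trial minimum, Protocol 5.1), 23 (closed-fracture SAP, abstract and 2.3) and 10 to show the effect of lower uptake. No ICC for troponin testing is given, so every ICC below is an assumption.

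**Step 1: reproduce the stated figure.** The half-width for independent patients is 1.96 × √(0.10 × 0.90 / 1,000) = 0.0186, or ±1.86 points, giving 8.1% to 11.9%. The Wilson interval is 8.3% to 12.0% and the Clopper-Pearson interval 8.2% to 12.0%. All round to 8% to 12%, so the plan's figure is the independent-patient one. Exactly ±2.00 points needs 1.96² × 0.09 / 0.02², or 865 patients.

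**Step 2: slack for clustering.** The half-width is multiplied by √DE, with DE = 1 + (m − 1) × ICC and m = 1,000 / number of sites (equal sizes). To stay within ±2 points, DE may not exceed (0.02 / 0.018594)² = 1.157. The largest tolerable ICC is therefore 0.157 / (m − 1):

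- 10 sites, m = 100: 0.157 / 99 = 0.0016
- 18 sites, m = 55.6: 0.157 / 54.6 = 0.0029
- 23 sites, m = 43.5: 0.157 / 42.5 = 0.0037

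**Step 3: a borrowed ICC.** The only between-hospital figures in the documents are for infection: variance 0.095 and ICC 0.028 (notes to Protocol Tables 5 and 6). The 0.028 is on the log-odds scale: 0.095 / (0.095 + π²/3) = 0.095 / 3.385 = 0.028. The design effect for a proportion needs the proportion scale, approximately 0.095 × p(1 − p) = 0.095 × 0.09 = 0.00855. At 18 sites, DE = 1 + 54.56 × 0.00855 = 1.466 and the half-width is 1.859 × √1.466 = 2.25 points.

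**Step 4: half-width in percentage points over a range of ICCs.**

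| Assumed ICC | 10 sites | 18 sites | 23 sites |
|---|---|---|---|
| 0 (the plan) | 1.86 | 1.86 | 1.86 |
| 0.00855 (infection variance) | 2.53 | 2.25 | 2.17 |
| 0.05 | 4.54 | 3.59 | 3.29 |
| 0.10 | 6.14 | 4.72 | 4.26 |

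At an ICC of 0.10 with 18 sites the interval is 5.3% to 14.7%, equivalent to about 155 independent patients. Unequal site sizes would generally widen these further.

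**The case against.** The sub-study is descriptive, no test or decision rule depends on ±2 points, and 1,000 is an expected number rather than a solved requirement. The only ICC that can be drawn from the documents belongs to a different outcome, and it moves the half-width only from 1.86 to about 2.2 or 2.3 with 18 to 23 sites. The larger figures come from chosen ICCs. Also, the objective is worded for PREPARE participants. If every site joined and inference stopped at those hospitals, sites would act as strata and the between-site component would largely drop out.

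Much of this stands: it limits the severity, and the true loss cannot be known from the documents. It does not rescue the wording. The size is said to depend on which sites join, the motive in 10.2 concerns fracture patients generally, and an assurance that fails at an ICC of about 0.003 to 0.004 needs a justification that the section does not give.

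A reader might go further and infer that the admission-to-day-3 window is wrong because a preoperative test would pass as monitoring for a postoperative injury. The documents do not support that. The stated objective is perioperative measurement, which the window matches. Item 1 is a data field, not a declared endpoint, and item 2 lets tests be placed before or after surgery. In the one high-sensitivity troponin T band where 10.1 requires a change between values, an earlier value could supply the comparison. A reader might also infer that this result is itself meant to steer screening policy; 10.6 assigns that role to the later cohort.

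**Conclusion.** The precision statement is not supported as written. It reproduces only under independence. With 18 to 23 equal-sized sites it fails once the ICC exceeds about 0.003 to 0.004. The infection variance, used as a stand-in, gives about ±2.2 to ±2.3 points; an assumed ICC of 0.10 gives about ±4.3 to ±4.7. Fewer sites widen it. These results rest on assumed ICCs, assumed numbers of sites, equal site sizes and the 10% working proportion.

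Two lesser points remain. Item 1 in 10.3 speaks of tests ordered where the objective in 10.2 speaks of levels measured. And no separate tabulation by timing is prespecified, although only a postoperative sample can show the postoperative peak that defines MINS in 10.1. The documents give no basis for estimating how many tests are preoperative only.

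The effect is confined to a descriptive sub-study. The trial's primary and secondary outcomes are unaffected, and the severity is minor.

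**What to change.** In 10.4 Sample Size, replace the assurance of precision within 2% with a cluster-adjusted range that states the assumed ICC and number of sites: for example, about ±2.3 points at an ICC of 0.009 and ±4.7 at 0.10 with 18 sites, with a line for lower uptake. In the sub-study SAP, specify that the reported interval will use a site-clustered method and that the number of sites and the estimated ICC will be reported. A clustered interval does not correct for sites being self-selected, so that should be stated as a limitation.

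As a minor addition, use the term measured in both 10.2 and 10.3. From the item 2 dates and times, report preoperative-only, postoperative-only and paired testing beside the stated perioperative proportion, without replacing it.

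The cost is a less favourable stated precision and a few lines of text. No patients, blood samples or data items are added.
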